### **7.2 Sample Size Considerations**

Approximately 6,000 pregnant women (of the 12,500 enrolled) admitted with the intent of delivery will be tested to detect 144 (2.4%) who are shedding HSV by PCR. A subject who enrolls on the study but does not have a vaginal specimen obtained will not count toward the target sample size. The process of determining the 6,000 to be tested by PCR is as follows: IDs of pregnant women enrolled in a given 3 month period (each quarter) will be randomly assigned by site to either (1) the group to be tested by PCR or (2) the group not to be tested by PCR. This will enable us to have better representation over time and across sites. Specimens will be collected and tested from an additional 300 nonpregnant women presenting to STI clinics with active herpetic lesions who are shedding HSV by both PCR and culture. A 95% confidence interval will be constructed for the sensitivity of Xpert HSV 1/2 Assay relative to culture for the nonpregnant women population. Since we do not anticipate many negative results in the

symptomatic nonpregnant population, we may not be able to estimate the specificity of the GeneXpert in this population. For the pregnant women population, 95% confidence intervals will be constructed for the true positive and negative percent agreement between Xpert and routine PCR. The sample size justification considers the width and lower bound of these 95% confidence intervals for a single proportion using Clopper-Pearson method (also known as the Fisher’s Exact CI) for small samples and large-sample confidence intervals for samples of greater than 100 (Ref Nonparametric Statistical Methods, Hollander and Wolf, Wiley, NY, NY 1973). SAS version 9.2 was used for these calculations.

Table 1 displays the minimum number of Xpert HSV 1/2 Assay positives from the total number of routine PCR positives in order to get a lower bound of a 95% confidence interval of at least 86%. With the expected 144 routine PCR positives from the pregnant women admitted with the intent of delivery, if the Xpert HSV 1/2 Assay finds 133 positives, then the corresponding 95% confidence interval for the true positive percent agreement will have a width of 9.4% and the resulting interval estimate is [86.7%, 96.1%]. Similar interpretations may be applied to the other cases considered in this table. With an expected 5856 negatives out of 6000 pregnant women, the 95% confidence interval for the negative percent agreement will be very tight. In particular, if the observed negative percent agreement is 97% (i.e., Xpert HSV 1/2 Assay finds 5680 negatives out of the 5856 routine PCR negatives), then the corresponding 95% confidence interval for the true negative percent agreement of Xpert HSV 1/2 Assay and routine PCR will have a width of 0.9% and the resulting interval estimate is [96.5%, 97.4%]. The reason for using positive and negative percent agreement instead of sensitivity and specificity is that routine PCR is not considered a gold standard.

Table 1: Minimum number of Xpert HSV 1/2 Assay positives, corresponding 95% Confidence Interval (CI) for Positive Percent Agreement, and width of the interval

Number of PCR Positives	135	137	139	142	144	150
Number of Xpert HSV 1/2 Assay Positives	124	126	128	131	133	138
Greatest number of Xpert HSV 1/2 Assay FN Allowed	11	11	11	11	11	12
95% CI for positive % agreement	85.9, 95.9	86.1, 95.9	86.3,96.0	86.6, 96.1	86.7, 96.1	86.4, 95.8
Width of CI	10.0	9.8	9.9	9.5	9.4	9.4

For nonpregnant women presenting to STI clinics with active herpetic lesions, Table 2 displays the minimum number of Xpert HSV 1/2 Assay positives from the total number of culture positives out of 300 subjects in order to get a lower bound of a 95% confidence interval of approximately 90%. Since we conservatively expect 270 of the 300 (90%) to be shedding HSV by culture, this is the smallest number of positive cultures considered in Table 2. To interpret, if

Xpert HSV 1/2 Assay finds 252 positives out of the 270 culture positives, the corresponding 95% confidence interval for the true sensitivity will have a width of 6.3% and the resulting interval estimate is [89.7, 96.0%]. Similar interpretations may be applied to the other cases considered in this table. The specificity of Xpert HSV 1/2 Assay may not be estimated in this population because we do not expect many culture-negative women. The main purpose of including this population is to enable us to get a precise estimate of the sensitivity of Xpert HSV 1/2 Assay relative to viral culture in women with symptomatic HSV lesions.

Table 2: Minimum number of positives and corresponding 95% Confidence Interval (CI) for Sensitivity

Number of Culture Positives	270	275	280	285	290	295	300
Number of Xpert HSV 1/2 Assay Positives	252	257	261	266	271	276	280
Greatest number of Xpert HSV 1/2 Assay FN Allowed	18	18	19	19	19	19	20
95% CI for sensitivity	89.7, 96.0	89.9, 96.1	89.6, 95.9	89.8, 95.9	90.0, 96.0	90.1, 96.1	89.9, 95.9
Width of CI	6.3	6.5	6.3	6.1	6.0	6.0	6.0

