## **7 STATISTICAL CONSIDERATIONS**

### **7.1 Study Hypotheses**

For pregnant women, we hypothesize that the long term expected positive percent agreement of HSV DNA using the Xpert HSV 1/2 Assay is 95% as evidenced by confidence interval containing this value. Therefore, with a sample size of between 135 and 150 we will have over a 95% probability of obtaining a point estimate greater than 91.8% with a lower bound of a 95% CI greater than 85%. This can be summarized in the form of hypothesis testing as:

$H_0$ : Positive Percent Agreement = 95%

$H_A$ : Positive Percent Agreement < 85%

Sample Size 135-150

Critical Value = 11FN, (or point estimate > 91.85% with lower 95% CI > 85%)

Target Alpha Value = 5%, Power > 95%.

For non-pregnant women, we hypothesize that the long term expected sensitivity of HSV DNA using the Xpert HSV 1/2 Assay is 95.34% as evidenced by a 95% confidence interval containing this value. Therefore, with a sample size of between 270 and 300 we will have a 95% probability of obtaining a point estimate greater 93.3% with a lower bound of a 95% CI greater than 90%. This can be summarized in the form of hypothesis testing as:

$H_0$ : Sensitivity = 95.34%

$H_A$ : Sensitivity < 90%

Sample Size 270-300

Critical Value = 18 false negative (FN), (or point estimate > 93.3% with lower 95% CI > 89%)

Target Alpha Value = 5%, Power > 95%.

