### 7.3 Participant Enrollment and Follow-Up

Subjects will be enrolled in one of two groups based upon their clinical status. Group 1 (n=300) will consist of women with clinically apparent herpetic genital lesions in STI Clinics. Group 2 (n=12,500) will consist of women without clinically apparent genital HSV lesions who are admitted with the intent of delivery. For women in Group 2, all study procedures will be uniform at each study site; once specimens from a given subject are received in the UAB Central Laboratory, the Study Biostatistician will randomly assign them to either batched processing by routine PCR or to storage for possible testing by PCR in the future. Those that are batch processed by routine PCR also will be analyzed subsequently by Xpert HSV 1/2 PCR. We anticipate that approximately half of women enrolled in Group 2 will have batched PCR analysis of their specimens performed, with the other half having their specimens stored.

Subjects in Group 1 and Group 2 are not seen in person after their involvement on Study Day 1. HSV culture results from women in Group 1 will be reported to their treating physician. Women in Group 2 or their designated representative will be contacted between Study Day 30 and Study Day 90 to assess for neonatal treatment for HSV infection and for maternal mode of delivery.

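### The single false-negative limits in Section 7.1 (18 and 11) do not hold the stated 95% probability across the ranges they are tied to, and the Group 1 range starts at its expected count

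*Combined protocol and SAP*

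**What the plan says.** **Section 7.1, Group 1.** Sensitivity is assumed to be 95.34%. The plan says "with a sample size of between 270 and 300 we will have a 95% probability of obtaining a point estimate greater 93.3" per cent, with a 95% lower bound above 90%. The summary block gives a critical value of 18 FN, or alternatively a point estimate above 93.3% with a lower limit above 89%. Target alpha is 5% and power above 95%. The null is 95.34% and the alternative is below 90%, so alpha here is the chance of failing a good assay.

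**Section 7.1, Group 2.** "Sample Size 135-150", positive percent agreement (PPA) 95%, and over 95% probability of success. The critical value is 11 FN, or a point estimate above 91.85% with a lower limit above 85%.

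**Section 7.2.** For Group 1 the authors "conservatively expect 270 of the 300 (90%) to be shedding HSV by culture, this is the smallest number of positive cultures considered" in Table 2. In Group 2 about 6,000 women "will be tested to detect 144 (2.4%) who are shedding HSV by PCR". The tables let the FN limit move with the count: 18 to 20 in Table 2, 11 to 12 in Table 1. The same section also describes the 300 Group 1 women as "presenting to STI clinics with active herpetic lesions who are shedding HSV by both PCR and culture".

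**Elsewhere.** Section 7.3 says "Group 1 (n=300) will consist of women with clinically apparent herpetic genital lesions in STI Clinics". Section 6.2 says that no laboratory test confirms eligibility. Sections 7.2 and 7.4 call for Clopper-Pearson intervals in small samples and large-sample intervals above 100. Section 4 keeps about half of the Group 2 specimens in storage so that enough PCR positives can be ensured.

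**The concern.** The denominators of sensitivity and PPA are not fixed by enrolment. They are the numbers of women whom culture or routine PCR happens to call positive. An FN limit that is right at one denominator is too strict at a larger one and too lenient at a smaller one, so one number cannot carry one probability over a range. In Group 1 the lower end of the range is also the expected count, so falling below it is an ordinary outcome at the planning rate, and Section 7.1 states nothing for that case. Both quantities are primary outcomes. At stake is whether the stated success rule and its 95% describe the design as it will run, and whether a reader can tell which rule applies at, say, 262 or 300 culture positives.

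**Working it through.** **Inputs.** Group 1: 300 enrolled, culture-positive rate 0.90, sensitivity 0.9534 (so FN rate 0.0466), boundary 0.90, limit 18 FN. Group 2: 6,000 tested, rate 0.024, PPA 0.95 (FN rate 0.05), limit 11 FN. All are from Sections 7.1 and 7.2.

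**1. Reproduce the plan.** Expected counts are 300 × 0.90 = 270 and 6,000 × 0.024 = 144. The Clopper-Pearson interval is 89.7-96.0% for 252/270 and 86.7-96.1% for 133/144, as printed; the Wald interval does not reproduce the tables. With pass probability P(FN ≤ c | n, q) from the binomial, P(FN ≤ 18 | 270, 0.0466) = 0.950, so alpha is 0.050. P(FN ≤ 18 | 270, 0.10) = 0.037, so power is 0.963. For Group 2, P(FN ≤ 11 | 135, 0.05) = 0.961. The stated figures hold at the bottom of each range.

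**2. Move up the ranges with the limit fixed.**

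| Group | Positives | Limit | Pass probability, good assay | 1 − pass (the plan's alpha) |
|---|---|---|---|---|
| 1 | 270 | 18 | 0.950 | 0.050 |
| 1 | 285 | 18 | 0.923 | 0.077 |
| 1 | 300 | 18 | 0.889 | 0.111 |
| 2 | 135 | 11 | 0.961 | 0.039 |
| 2 | 144 | 11 | 0.942 | 0.058 |
| 2 | 150 | 11 | 0.926 | 0.074 |

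With the table limits at the top of each range, 20 FN of 300 gives 0.957 and 12 FN of 150 gives 0.961. At 144, Table 1 itself allows 11, so the expected Group 2 count gives 0.942 either way.

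**3. Group 1 lower bound above 90%.** By the exact method, 18 FN of 270 gives 89.7%, so at most 17 FN are allowed: P(FN ≤ 17 | 270, 0.0466) = 0.917. At 300 the limit is 19 FN and the probability 0.929. With a Wald interval, 18 FN of 270 gives a lower bound of 90.4%, which restores 0.950.

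**4. Chance of reaching the ranges.** Group 1 positives follow Binomial(300, 0.90): SD = √(300 × 0.9 × 0.1) = 5.2, 5th percentile 261, P(at least 270) = 0.548, so P(fewer than 270) = 0.452. Group 2 positives follow Binomial(6,000, 0.024): SD 11.9, P(at least 135) = 0.787, P(135 to 150) = 0.499.

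**5. Average over the random count**, Σ P(N = n) × P(pass | n):

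| Rule | Average probability |
|---|---|
| Group 1, 18 FN | 0.949 |
| Group 1, exact lower limit above 89% | 0.970 |
| Group 1, exact lower limit above 90% | 0.907 |
| Group 1, Wald lower limit above 90% | 0.956 |
| Group 2, 11 FN | 0.937 |
| Group 2, exact lower limit above 85% | 0.978 |

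**6. Lower Group 1 yields (an assumption; the documents give only 90%).** For an assay at 90% sensitivity, P(FN ≤ 18) is 0.037 at 270 positives, 0.055 at 260 and 0.116 at 240 (80% yield). With exact intervals, the average probability of a lower limit above 89% / above 90% at 95.34% sensitivity is 0.95 / 0.86 at 80% yield and 0.92 / 0.80 at 70%.

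**The case against.** The strongest reply is that Section 7.1 does not give a bare FN count. The same line offers a point-estimate and confidence-limit form, and the tables vary the limit with the count. Read that way, 18 FN of 240 does not pass (estimate 92.5%, exact lower limit 88.4%), and 20 FN of 300 does. This stands as far as it goes. What remains is that the two forms disagree inside the stated range (18 against 20 at 300), the text does not say which governs, and at the expected 144 in Group 2 both give 0.942, not over 95%.

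Second, the primary objectives are to estimate, and Section 7.4 reports confidence intervals with no pass/fail test, so no planned analysis fails at 262 positives. True, and it limits the consequence to the stated criterion and its probability.

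Third, large-sample intervals are prescribed above 100, and a Wald interval gives about 0.95 for a lower bound above 90%. Also true, but Tables 1 and 2 use exact intervals at counts above 100, and Section 7.1 names no method and gives both 90% and 89%.

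A reader might also infer more than the documents support:

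- **That Group 2 reaches its count only half the time.** The 0.499 treats counts above 150 as misses, although they improve precision. At least 135 is reached with probability 0.79, and stored specimens are an explicit reserve.
- **That Group 1 loses its protection against a poor assay.** At 90% yield an assay at 90% sensitivity passes 18 FN with average probability 0.038. Material loss needs yields near 80%, which nothing in the documents suggests; the plan calls 90% conservative.
- **That the plan asserts 270 as the least possible count.** It says only that 270 is the lowest count shown in Table 2.

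**Conclusion.** The point holds in a limited form. Section 7.1's single FN limits meet the stated 95% at the bottom of each range and miss it higher up: 0.889 at 300 in Group 1, and 0.942 and 0.926 at 144 and 150 in Group 2. They also differ from the limits in Tables 1 and 2. The Group 1 sentence that pairs 95% with a lower bound above 90% is not true with the exact intervals used in the tables (0.917 at 270, 0.907 on average).

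The Group 1 range is missed 45% of the time at the planning rate, with no reserve stated. This applies to Group 1 only. It rests on reading the 300 as women enrolled on lesions; if they are 300 women already positive by culture and PCR, the shortfall disappears, but 270 of 300 then cannot stand. At 90% yield the average effect is small, and the documents do not support calling the study too small. The results assume independent binomial counts and the plan's own rates.

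**What to change.** - In Section 7.1, make a lower-confidence-limit criterion at the realised number of comparator positives the governing rule, with one threshold and one named interval method per group. Keep 18 and 11 FN only as illustrations at particular counts, consistent with Tables 1 and 2.
- Restate the probability. For Group 1 with exact intervals it is about 0.97 for a lower limit above 89% or about 0.91 for above 90%; for Group 2 it is about 0.98 for above 85%. The choice is a trade-off. With the 89% threshold alone, 19 FN of 270 would pass, and an assay at 90% sensitivity passes with probability P(FN ≤ 19 | 270, 0.10) = 0.059; with 90% (17 FN) it is 0.022. If the 93.3% point-estimate condition is kept as well, it governs, and the average falls to about 0.94.
- Extend Table 2 below 270, for example to about 255.
- Reconcile the two statements in Section 7.2: 300 women shedding by both PCR and culture, and 270 of 300 positive by culture.
- State when stored Group 2 specimens would be drawn on; no trigger is given now.

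The cost is protocol wording and a longer table. The stated Group 1 probability becomes slightly less favourable if the 90% threshold is kept with exact intervals. No extra enrolment is needed, because the rule then applies at any count.

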### 7.3 Participant Enrollment and Follow-Up

Subjects will be enrolled in one of two groups based upon their clinical status. Group 1 (n=300) will consist of women with clinically apparent herpetic genital lesions in STI Clinics. Group 2 (n=12,500) will consist of women without clinically apparent genital HSV lesions who are admitted with the intent of delivery. For women in Group 2, all study procedures will be uniform at each study site; once specimens from a given subject are received in the UAB Central Laboratory, the Study Biostatistician will randomly assign them to either batched processing by routine PCR or to storage for possible testing by PCR in the future. Those that are batch processed by routine PCR also will be analyzed subsequently by Xpert HSV 1/2 PCR. We anticipate that approximately half of women enrolled in Group 2 will have batched PCR analysis of their specimens performed, with the other half having their specimens stored.

Subjects in Group 1 and Group 2 are not seen in person after their involvement on Study Day 1. HSV culture results from women in Group 1 will be reported to their treating physician. Women in Group 2 or their designated representative will be contacted between Study Day 30 and Study Day 90 to assess for neonatal treatment for HSV infection and for maternal mode of delivery.

## **8 SOURCE DOCUMENTS AND ACCESS TO SOURCE DATA/DOCUMENTS**

Documentation of source data is necessary for the reconstruction, evaluation, and validation of clinical findings, observations, and other activities during a clinical trial. Source documentation serves to substantiate the integrity of the trial data, to confirm observations that are recorded, and to confirm the existence of study participants. This standard also serves to ensure data quality by creating audit trails and enabling verification that data are present, complete, and accurate. This study will be monitored using these standards.

The site will maintain appropriate medical and research records for this trial, in compliance with ICH E6, Section 4.9 and regulatory and institutional requirements for the protection of confidentiality of subjects. As part of participating in a DMID-sponsored, DMID-affiliated, or manufacturer-sponsored study, the site will permit authorized representatives of the sponsor(s), DMID, the UAB Central Unit, and regulatory agencies to examine (and when required by applicable law, to copy) clinical records for the purposes of quality assurance reviews, audits, and evaluation of the study safety and progress.

Examples of these original documents and data records may include, but are not limited to, Source Document Worksheets, hospital records, clinical and office charts, recorded data from automated instruments, and subject files and records kept at the laboratories.

Sites that are participating in this trial should consult the MOP and DMID/NIAID Source Document Standards (most current version) for specific instruction and forms.

The study monitor or other authorized representatives of the sponsor, or other governmental regulatory agencies may inspect all documents and records required to be maintained by the investigator for this trial. The clinical study site will permit access to such records.

## **9 QUALITY CONTROL AND QUALITY ASSURANCE**

The study site will implement a quality management plan. The quality management procedures are described herein, as well as in the Manual of Procedures and the study site quality management plan (QMP). Per the QMP, data will be evaluated for compliance with the protocol and accuracy in relation to source documents. The study will be conducted in accordance with procedures identified in the protocol. Items to be reviewed include, but are not limited to: eligibility (including informed consent), any required AE reporting, study/clinical endpoints, follow-up visits, regulatory documents, missed calls, and review of clinical records. Data that will be reviewed, who is responsible for implementation, and the schedule for internal reviews will be specified or referenced in the quality management plan.

The UAB Statistical and Data Coordinating Center will implement quality control procedures beginning with the data entry system, and will generate data quality control checks that will be run on the database within 24 hours of new data entered into the system. Full documentation of these checks will be provided to the UAB Central Unit so that any resulting queries can easily be understood and transmitted to the respective site for resolution within a short period of time. These processes are validated by a second programmer and also tested with faulty test data (refer to Section 13 for additional details).

Site monitoring will also be implemented by a DMID directed independent monitoring group. See Section 12 (*Clinical Monitoring Structure*) for additional details.

## **10 SUBJECT CONFIDENTIALITY**

The information obtained during the conduct of this clinical study is confidential, and disclosure to third parties other than those noted below is prohibited. The results of the research study may be published, but study participant's names or identities will not be revealed. Records will remain confidential. To maintain confidentiality, the principal investigators at each site will keep records in locked cabinets and the results of tests will be coded to prevent association with volunteers' names. Data entered into computerized files will be accessible only by authorized personnel directly involved with the study and will be encoded. Data received by DMID and forwarded to Cepheid will not include subject specific data but only encoded data. However, subject specific information will be available to the clinical monitors, and to health authorities where provided by law.

The study investigator is obliged to provide the NIAID/DMID and the UAB Central Unit with complete test results and all data developed in this study. The NIAID/DMID or the UAB Central Unit may disclose this information to appropriate regulatory authorities or clinical practice management groups (such as Pediatric Infectious Disease Society) as deemed necessary by the NIAID/DMID or the UAB Central Unit.

Subject-specific information may be provided to other appropriate medical personnel only with the study participant's permission. To ensure compliance with current ICH guidelines, data generated by this study must be available for inspection upon request by representatives of national and local health authorities, NIAID/DMID, the UAB Central Unit, and the Central Facilitated IRB/IEC overseeing the study (or for each study site, if the site does not utilize the Central Facilitated IRB).

### **10.1 Future Use of Stored Specimens**

Approximately half of the 12,500 women enrolled in Group 2 will have their specimens stored for possible future HSV testing by PCR and serology. This will be fully explained in the Informed Consent document and will not be subject to "Future Use of Specimens" documentation since this testing is the primary purpose of the study. Likewise, any additional comparator PCR assays for HSV DNA that might be required by the FDA for this study will not be subject to "Future Use of Specimens" documentation since this comparison is the primary purpose of the study.

Subjects will be asked at the time of enrollment for permission to keep any remaining specimens for possible future use. Some of the specimens obtained from study participants during this study will be stored indefinitely in the UAB Central Laboratory at the University of Alabama at Birmingham and may be used in future viral or other sexually transmitted infection

research. These specimens will be labeled with a code number and not with the study participant's name. At the time of consent for study participation, study participants will have the opportunity to either agree to have their specimens used in future research or decline to have their specimens used in future research. The study participant will indicate her preference by initialing the appropriate line or checking the appropriate box of the Consent Form in the section entitled, "Future Use of Specimens". Non-protocol designated, future testing of samples will be performed only on samples from study participants who have consented for future testing of samples.

Samples may be shared with other investigators at other institutions or with the manufacturer of the GeneXpert cartridge. The samples will not be sold or used directly for production of any commercial product. No human genetic tests will be performed on samples. Long term storage of residual samples will be established according to OHRP guidelines ensuring that codes or other personally identifying links will not be distributed to future researchers.

The specimens will be stored indefinitely in the UAB Central Virology Laboratory at the University of Alabama at Birmingham. Specimens from study participants will be labeled and coded without study participant's identifiers. If the study participant has indicated in the signed consent form that she does not agree to allow the future use of specimens for future research, then her specimens will be destroyed at the completion of the study.

